RESEARCH PROTOCOL OUTLINE

Title of Project: Mobile Health Study and Enhanced Symptom Monitoring to Prevent Severe Illness from COVID-19 in Cancer Patients

Principal Investigators: [name]., Department of OB/GYN
[name], Dept. of Family and Preventive Medicine

Co-Investigators: [name], College of Public Health

Abstract

The severe acute respiratory syndrome corona virus 2 (SARS-CoV-2) outbreak in late 2019 has resulted in over 4.28 million confirmed cases of novel coronavirus disease (COVID-19), with over 292,000 confirmed deaths worldwide (as of May 13, 2020). Severe disease occurs in ~10% of cases overall. However, risk for severe disease and mortality is greater in immunocompromised cancer patients, requiring scarce ventilation resources and intensive care unit space to address rapid clinical deterioration in this population. We propose to use the established Insight™ mHealth Platform, a component of the Stephenson Cancer Center (SCC) mHealth Shared Resource, to create the “Symptom Tracker” app. The Symptom Tracker (Insight™) app will enable real-time monitoring of cancer patient symptoms that are consistent with early signs of SARS-CoV-2 infection in this high-risk population by automatically (and securely) transferring this information to health care providers. The primary aim of this study is to determine the feasibility, ease of use, and perceived utility of this app to monitor symptoms and health risk behaviors among cancer patients currently receiving chemotherapy. Health risk behaviors, standard COVID-19 screening questions, and a single chemotherapy risk question will be assessed daily through the smartphone app. Specific responses will automatically trigger an alert to clinic nurses AND provide app-based access to contact the clinic for triage to home care or emergency assessment. When/if study participants screen positive for COVID-19, they will receive a device to measure their pulse and blood oxygen levels daily. This information and COVID-19 symptoms will be monitored daily via the Symptom Tracker (Insight™) app. This study will determine if an app can be used to rapidly report COVID-19 symptoms and quickly intervene to reduce morbidity and mortality in immunocompromised cancer patients. Further, data from this study will be used to inform the development of future mHealth interventions that will be tested in fully powered randomized control trials.

A. Specific Aims

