The primary objective of this research is to use innovative mHealth technology to monitor symptoms in real-time and facilitate medical triage of high-risk patients. The current study will obtain data on the feasibility of an innovative mHealth application to track symptoms and automatically intervene upon reported high-risk symptoms among cancer patients who are receiving cytotoxic chemotherapy or immunotherapy treatments. This objective will be attained by pursuing the following specific aims:

1. Determine the feasibility, ease of use, and perceived utility of the Symptom Tracker (Insight™) mHealth app to monitor symptoms and health risk behaviors for up to 500 patients who are receiving chemotherapy to treat cancer.
 - a. On average, participants will complete >50% of all prompted daily phone based ecological momentary assessments (EMAs).

- b. Most participants will report that the app is easy to use, and provides useful information (assessed quantitatively and qualitatively during the 24-week phone based or RedCap follow-up interview).
2. Examine participant characteristics and outcomes of those who do and do not test positive for COVID-19 during the 24-week monitoring period.
 - a. Among those who undergo enhanced monitoring, we will use descriptive statistics to summarize the proportion of patients experiencing the following outcomes: manifestations of severe disease, treatment related toxicity, need for hospitalization, and SARS-CoV-2 related mortality.
 - b. We will also compare outcomes and tolerability of enhanced self-monitoring for severe infection and compare rates of disease related morbidity and mortality to baseline rates published in the literature.
 - c. We will use quantitative and qualitative methods to evaluate participant satisfaction with the app among those who test positive for COVID-19 and are asked to report vital signs each day.
3. Collaboratively document and share lessons learned regarding the impact of the COVID-19 pandemic on cancer care delivery via telemedicine and mHealth technology. We commit to a collegial collaboration with other cancer centers funded to study the use of telemedicine through the COVID-19 CCSG supplement mechanism.

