As a practicing oncologist within Stephenson Cancer Center, [name], Ph.D. is knowledgeable about the medical needs of the population that is being recruited for this study, and she regularly uses evidenced-based interventions to treat cancer. Her research and clinical experience complement [name] experience with research using mobile technology for health improvement. Additional study investigators include [name] (biostatistician) and [name] (basic and translational scientist) have agreed to assist with study recruitment and follow-up procedures.

D. Research Design and Methods

Study Design: A total of 500 treatment-seeking males and females will be asked to complete daily monitoring of symptoms and weekly monitoring of health risk factors weekly via smartphone app (Aim 1). Those who screen positive for COVID-19 will be triaged to emergency or non-emergency medical treatment. COVID-19 positive patients identified for non-emergent medical treatment will receive a study-supplied device to measure their oxygen level and heart rate and be instructed in the device's use. They will be prompted to enter vital signs data daily (such as body temperature, oxygen level, and heart rate) and questions from the app will change to assess the severity of COVID-19 related symptoms and inform changes in level of care, to emergency or non-emergency medical management as indicated by self-reporting. The proposed study will assess the impact of heightened symptom and vital sign monitoring on the early identification of severe manifestations of COVID-19 in this high-risk population (Aim 2). It is hypothesized that this will significantly improve COVID-19 related morbidity and mortality compared to the national and international rates currently reported in the literature. Figure 1 displays the participant flow through this 24-week study.

The SCC mHealth Shared Resource has created the versatile and reusable Insight™ mHealth Platform. Insight™ is HIPAA compliant and data are encrypted within the app. There will be 4 sources of data for the current study: 1) in-person data collected in a private room at the SCC

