When participants provide a pattern of responses that are suggestive of heightened risk for COVID-19 (See algorithm in Appendix), they will receive a suggestion to contact SCC staff, and the app will send an encrypted email containing this information to [name] and other SCC staff with a request to contact the participant to assess symptoms (see Appendix) and whether urgent medical attention is indicated. Should urgent medical attention be warranted, the patient will be instructed to the clinical unit most appropriate to the symptoms they reported through the app algorithm or discussed with the clinical nursing or physician staff. Non-emergent patients who screen positive for COVID-19 will begin an enhanced symptom and vital sign monitoring period that will continue until the participant reports that they are no longer symptomatic and/or a medical professional informs them that they no longer need to self-quarantine, which is expected to be approximately 21 days. These patients will receive a pulse oximeter (provided by the study) and the app questions will change to include daily prompts requesting that the patient input morning vital signs (temperature, heart rate, blood oxygen levels (SpO2)) and answer questions specific to the severity of symptoms and/or emergence of new symptoms of COVID-19. If a patient is hospitalized, they can continue to complete the daily assessments if they are willing and able to do so. The app will also support check-ins with SCC staff and after-hours medical staff as needed after diagnosis of COVID-19 or until the patient has been medically released from self-quarantine. Once the participants have completed the enhanced symptom and vital sign monitoring portion of the study, the pulse oximeter will be returned to the research team at the time of their next scheduled appointment. These devices will then be sterilized with both alcohol-based sanitizing products as well as ultraviolet light exposure in accordance with practices endorsed by the Centers for Disease Control.

Participants will continue to use the app to complete a final 24-week follow-up survey and will be contacted by phone (or RedCap if a medical condition prevents them from being able to speak for long periods of time) to complete a brief qualitative interview 24 weeks after study enrollment. Relevant demographic, cancer-specific and COVID-19 related data will be extracted

from electronic health records at the conclusion of the study.

E. Chart Review

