Aim 2. We will examine participant characteristics among those who are and are not transitioned to an Aim 2 monitoring of vital signs and severity of COVID-19 symptoms. We will also examine participant characteristics and outcomes for those that require emergent intervention versus non-emergent intervention. Among those who undergo enhanced monitoring, we will use descriptive statistics to summarize the proportion of patients experiencing the following outcomes: manifestations of severe disease, treatment related toxicity, need for hospitalization, and COVID-19 related mortality. We will also compare outcomes and tolerability of enhanced self-monitoring for severe infection and compare rates of disease related morbidity and mortality to baseline rates published in the literature. We will evaluate participant satisfaction with the app and identify ways to improve this novel patient monitoring technology. We will perform logistic regression to determine the odds of experiencing primary outcomes, based upon baseline characteristics (e.g., sex, race/ethnicity, cancer stage/type). Kaplan-Meier survival curves and log-rank tests of homogeneity will be used to identify the survival functions, describing the time to resolution of symptoms based upon

demographic characteristics. Because COVID-19 is a novel virus and we do not fully understand its impact on our patient population, this study will provide useful, granular information about the daily symptoms of and recovery from COVID-19 in cancer patients.

Aim 3. No analyses proposed, as this is a collaboration aim.

N. Data and Safety Monitoring Plan

Data quality and integrity will be held to the highest standard to ensure accurate reporting and documentation of the objectives outlined in the proposal. The Institutional Review Board and the Office of Clinical Research will monitor data and safety monitoring. The institutional plan for data and safety monitoring for all trials funded by the NCI has been adopted by the University and will be utilized for conduct of our planned proposal.

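### Aim 2's comparison with published COVID-19 rates does not fix its analysis set; its most direct reading uses only non-emergent positives, which can look like a benefit when there is none

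*Combined protocol and SAP*

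**What the plan says.** All references are to the combined protocol and SAP.

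- **The comparison.** Section M, Aim 2, will "compare rates of disease related morbidity and mortality to baseline rates published in the literature". Aim 2b in Section A has the same plan: "We will also compare outcomes and tolerability of enhanced self-monitoring for severe infection and compare rates of disease related morbidity and mortality". Neither place names the participants to be counted, the published source, or a test or threshold.
- **The sentence before it in Section M.** "Among those who undergo enhanced monitoring, we will use descriptive statistics to summarize the proportion of patients experiencing the following outcomes". The outcomes listed include severe disease, hospitalization and COVID-19 death.
- **Who enters enhanced monitoring, narrow version.** Section D, Study Design: "COVID-19 positive patients identified for non-emergent medical treatment will receive a study-supplied device to measure their oxygen level and heart rate". Section D, Study application: "Non-emergent patients who screen positive for COVID-19 will begin an enhanced symptom and vital sign monitoring period".
- **Who enters enhanced monitoring, wide version.** Abstract: "When/if study participants screen positive for COVID-19, they will receive a device to measure their pulse and blood oxygen levels daily". In Section D, Measures, any participant who contracts the virus presses an app button and gets the enhanced questions. Neither place sets a triage condition.
- **The hypothesis.** Section D, Study Design, expects monitoring to improve morbidity and mortality significantly over national and international rates. It does not say whether those are rates in cancer patients.
- **Candidate benchmarks.** Section B gives severe disease in about 10% of all cases. For cancer patients it gives close to 40% severe and up to 20% mortality. None is designated as the comparator.
- **Emergent patients.** Section M also states: "We will also examine participant characteristics and outcomes for those that require emergent intervention versus non-emergent intervention".

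**The concern.** Triage to emergency care is a severity filter applied when infection is identified. If the study rate is calculated only in those who pass it, and the published rate covers everyone infected, the two rates describe different populations. When the removed patients have a worse than average outcome, the study rate is lower for that reason alone.

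Section D attaches a directional hypothesis of significant improvement to this comparison, Section A plans to use the data to pursue R01 funding, and Section O plans publication. A lower rate in the monitored group could be reported as support for the app when it reflects only who was counted. Because the text supports two analysis sets and several benchmarks, the choice could also be made after the data are seen.

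**Working it through.** The plan gives no figure to reproduce. It states no expected number of infections, emergent share, benchmark, test or alpha for this comparison. The calculation below shows direction and possible size under stated assumptions.

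**Step 1. The two analysis sets.**

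| Set | Support in the text |
|---|---|
| Non-emergent positives | The comparison directly follows the enhanced-monitoring sentence in Section M; Aim 2b itself mentions enhanced self-monitoring; Section D (Study Design, Study application) limits that monitoring to non-emergent positives |
| All positives | Aim 2 in Section A is framed on those who do and do not test positive; the exploratory literature comparisons in Section A refer to those who test positive or contract the virus; the Abstract and Section D, Measures, set no triage limit |

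**Step 2. Rate in the non-emergent set with no app effect.** Let R be the true rate in all positives, e the emergent share and p the event rate in emergent patients. Then

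non-emergent rate = (R − e·p) / (1 − e).

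R = 0.40 is the Section B background figure, used as both true rate and benchmark. The values of e and p are assumptions.

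- e = 0.20, p = 0.40: (0.40 − 0.08)/0.80 = 0.400 (no bias)
- e = 0.10, p = 0.60: (0.40 − 0.06)/0.90 = 0.378
- e = 0.20, p = 0.60: (0.40 − 0.12)/0.80 = 0.350
- e = 0.20, p = 0.80: (0.40 − 0.16)/0.80 = 0.300

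**Step 3. Chance of an apparent benefit.** Assume 50 infected, and call it a benefit when the exact (Clopper-Pearson) 95% upper limit is below 40%. The plan contains no such rule; it is used here only to give a scale. The rule is met with at most 9 events of 40, or 11 of 45. Each scenario is compared with no bias at the same n, because the discreteness of the binomial changes the baseline.

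| Scenario | n | Rate | Chance of apparent benefit | Same n, rate 40% |
|---|---|---|---|---|
| e = 10%, p = 60% | 45 | 37.8% | P(X ≤ 11) = 4.2% | 2.2% |
| e = 20%, p = 60% | 40 | 35% | P(X ≤ 9) = 6.4% | 1.6% |
| e = 20%, p = 80% | 40 | 30% | P(X ≤ 9) = 19.6% | 1.6% |

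With all 50 positives counted and a true rate of 40%, the chance is P(X ≤ 12) = 1.3%.

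**Step 4. What would cancel the bias.** The non-emergent rate equals 40% when this cohort's true rate in all positives is 0.40·(1 − e) + e·p. That is 0.36 + 0.06 = 42%, 0.32 + 0.12 = 44% and 0.32 + 0.16 = 48% in the three scenarios. Participants are all on active chemotherapy or immunotherapy (Section H), so a true rate above the benchmark is possible.

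**Step 5. Precision.** With all positives and 40% severe, the exact 95% interval is 26.4% to 54.8% for 20/50.

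**Step 6. Comparator.** A severe rate of 25%, for example, lies below the 40% quoted for cancer patients and above the 10% quoted for all cases. The direction of the conclusion therefore depends on a choice the plan leaves open.

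**The case against.** The strongest reply is that the non-emergent set is only one reading. In Section A the enhanced-monitoring sentence is item 2a and the comparison is a separate item, 2b, under an aim framed on testing positive; in Section M it is a new sentence. This stands as far as it goes: the narrow set is not an established plan. But 2b refers to enhanced self-monitoring, and nothing in Section M directs the analyst to all positives.

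Patients who worsen after entering enhanced monitoring still count, and Section D lets hospitalized patients continue the daily assessments. This also stands. The selection concerns only those who are already emergent at triage.

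The probabilities belong to a decision rule the plan does not contain, with an assumed benchmark, emergent share, emergent event rate and number infected. That is correct, and the milder scenarios are small: 4.2% against 2.2% with 10% emergent.

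The stakes are limited. Feasibility is the primary aim, Section A calls the reduction in severe disease something to explore, and the Abstract leaves testing to future randomized trials. Section M already plans to examine emergent against non-emergent outcomes, so rates in all positives can probably be derived. That lowers the severity, but it does not say which set meets the benchmark.

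A reader might also infer that the counting window is contradictory, because Section D, Measures, gives 21 days while the Study application text says monitoring "will continue until the participant reports that they are no longer symptomatic" or until a medical professional ends quarantine. The documents do not support that. Both texts govern how long the enhanced prompts run, and the second expects about 21 days, so they largely agree.

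**Conclusion.** The point holds as a possibility created by the text. The most direct reading of Aim 2 can set a triage-selected group against rates from all infected patients, and that lowers the study rate without any app effect if emergent patients do worse than average. A reader might infer that the plan will produce a false benefit, or that emergent patients are certainly excluded. The documents show neither. The bias is zero if emergent patients have the average rate, and a higher true rate in this on-treatment cohort could cancel it. The denominator behind the 40% and 20% in Section B cannot be checked here.

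The size cannot be computed from the documents. The largest hypothetical shown, 19.6% against 1.6%, needs a 20% emergent share with an 80% severe rate among them; the others are modest. Counting all positives removes only the triage selection. The comparison stays historical and uncontrolled, in consenting participants who meet a literacy requirement and are screened daily by the app. The issue is minor to moderate, on a secondary aim, and worth correcting because of the hypothesis in Section D and the planned use of the data.

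**What to change.** - **Section M, Aim 2 (and Aim 2b).** Define the set for the literature comparison as all enrolled participants with a confirmed positive test, emergent and non-emergent together. Report the enhanced-monitoring subset separately. Name one published comparator in cancer patients, state its population and denominator, and give exact 95% confidence intervals for the study rates.
- **Section D, Study Design.** Replace the expectation of significant improvement with a descriptive, hypothesis-generating statement. Say that the comparison is uncontrolled and that participants are consenting, literate and app-screened.
- **Abstract and Section D, Measures, against Section D, Study Design and Study application.** Reconcile these on who enters enhanced monitoring. Which rule applies is for the study team.

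The cost is wording. The team should confirm that severity, hospitalization and death are captured for every positive participant. The items printed in Section E do not name them, but that section refers to an appendix that is not shown, and Section D plans extraction of COVID-19 related data from the health record, so this is a check and not a claimed gap. The downside is a comparison that may look less favourable.

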This study will also explore the potential reduction of severe COVID-19 mediated disease through: 1) reducing time from symptom detection to treatment initiation (i.e., comparing treatment initiation times among those who test positive for COVID-19 in this study to published literature), and 2) closely monitoring COVID-19 symptoms among those who contract the virus (i.e., again, comparing participants in this study to published literature). COVID-19 is a novel virus and we do not fully understand its impact on our patient population. This study will provide useful, granular information about the daily symptoms of and recovery from COVID-19 in cancer patients. Data from this study will be used to pursue NIH R01 funding to formally evaluate the effects of using mHealth technology to monitor symptoms and health risk factors and intervene in real-time.

B. Background and Significance

The severe acute respiratory syndrome corona virus 2 (SARS-CoV-2) outbreak in late 2019 has resulted in approximately 4.28 million confirmed cases of novel coronavirus disease (COVID-19), with over 292,000 confirmed deaths worldwide (as of May 13, 2020)[1]. The United States has reported the greatest number of cases across the world, with a total of 1.4 million new cases and over 83,000 attributable deaths as of May 13, 2020. Severe disease accounts for approximately 10% of cases and adds tremendous burden on limited medical resources and medical personnel.

Risk factors for severe disease are largely unknown, but clinical experience suggests that persons over age 65 with co-morbid conditions, such as immunosuppression from cancer or chemotherapy, place cancer patients in the “high-risk” group for severe manifestations of COVID-19 mediated disease [2]. Therefore, cancer patients are likely at increased risk for COVID-19 infection and may have a poorer prognosis. According to recent data, the risk of severe infection in cancer patients approaches 40% with up to a 20% mortality rate [3]. Thus, there is increased need for invasive ventilation and intensive care unit admission to circumvent rapid clinical deterioration in this population. Novel methods are needed to remotely monitor for SARS-CoV-2 infection and rapidly intervene to reduce morbidity and mortality in cancer patients exhibiting symptoms of the virus. Given evidence of poor outcomes in cancer patients, early intervention may significantly improve outcomes.

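### Section M plans Kaplan-Meier curves for time to symptom resolution without saying how death before resolution is handled; if deaths are censored, the curves overstate the proportion recovered

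*Combined protocol and SAP*

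**What the plan says.** Section M (Aim 2) states that "Kaplan-Meier survival curves and log-rank tests of homogeneity will be used to identify the survival functions, describing the time to resolution of symptoms", by demographic characteristics. Among patients under enhanced monitoring, the same paragraph will summarize severe disease, treatment toxicity, "need for hospitalization, and COVID-19 related mortality". It gives the purpose as follows: "this study will provide useful, granular information about the daily symptoms of and recovery from COVID-19 in cancer patients".

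Section B says of cancer patients that "the risk of severe infection in cancer patients approaches 40% with up to a 20% mortality rate". Under Study application, Section D limits entry to the less urgent cases: "Non-emergent patients who screen positive for COVID-19 will begin an enhanced symptom and vital sign monitoring period".

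The length of follow-up is described in two ways. The text after Table 1 in Section D gives 21 days, after which the app returns to its usual questions. Study application lets monitoring run until the participant reports no symptoms and/or a medical professional ends the self-quarantine, which is expected to take about 21 days.

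On data sources, Study application says "If a patient is hospitalized, they can continue to complete the daily assessments if they are willing and able to do so". It also plans a health-record extraction: "Relevant demographic, cancer-specific and COVID-19 related data will be extracted". Section E shows 16 chart items. Date of death is not among them, but the full list is in an Appendix that is not in the available text.

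No available section gives a censoring rule for this analysis, names a competing event or mentions cumulative incidence.

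**The concern.** A patient who dies with symptoms can no longer recover. Kaplan-Meier with that death censored treats the patient as still able to recover at the same rate as those who remain. One minus the curve then estimates recovery in a setting without death, which is higher than the proportion of patients who actually recover.

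The plan itself foresees deaths in this group, and describing recovery is a stated purpose. With similar resolution rates, the overstatement is larger where more patients die. Two demographic groups with different real recovery can therefore show the same curve. A larger sample reduces the noise but not this bias.

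**Working it through.** The plan gives no event count, resolution rate, death timing or power for this analysis, so there is no figure to reproduce. The only documented input on size is the upper mortality of 20% in Section B. Everything else below is assumed. The time point is day 21.

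**1. Constant hazards.** Let r and d be the daily hazards of resolution and death, s = d/(r+d) the share of first events that are deaths, and F = 1 − exp(−21(r+d)) the proportion resolved or dead by day 21.

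- True proportion resolved: (1 − s)F.
- One minus Kaplan-Meier, deaths censored: 1 − exp(−21r) = 1 − (1 − F)^(1−s).
- Standard error: √(p(1 − p)/n), with p the true proportion and n an assumed 50 or 25 positives.

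| s | F | True | 1 − KM | Excess (points) | SE, n=50 / n=25 |
|---|---|---|---|---|---|
| 5% | 60% | 57.0% | 58.1% | 1.1 | 7.0 / 9.9 |
| 5% | 90% | 85.5% | 88.8% | 3.3 | 5.0 / 7.0 |
| 10% | 60% | 54.0% | 56.2% | 2.2 | 7.1 / 10.0 |
| 10% | 90% | 81.0% | 87.4% | 6.4 | 5.5 / 7.8 |
| 20% | 60% | 48.0% | 52.0% | 4.0 | 7.1 / 10.0 |
| 20% | 90% | 72.0% | 84.2% | 12.2 | 6.3 / 9.0 |

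The excess is below one standard error throughout at 5%. At 10% it exceeds it only with F = 90% and n = 50. At 20% it exceeds it when F = 90%.

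**2. Late deaths.** Assume recovery uniform over days 5 to 25 among survivors, eventual mortality m, and deaths uniform over days a to b. By day 21, 16/20 = 80% of survivors have resolved, so the true proportion is 0.80(1 − m). One minus Kaplan-Meier is 1 − exp(−∫ [(1 − m)/20]/S(t) dt) over days 5 to 21, where S(t) = 1 − (1 − m)(t − 5)/20 − m·max(0, (t − a)/(b − a)).

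- Deaths over days 14 to 40, with m = 5%, 10%, 20%: 76.0 vs 76.5, 72.0 vs 72.9 and 64.0 vs 65.5, an excess of 0.5, 0.9 and 1.5 points.
- Deaths over days 10 to 30: an excess of about 1.3, 2.5 and 4.5 points.

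**3. A less favourable setting.** The ranges above are not bounds. Here mortality means the proportion already dead by day 21, with 2% to 20% still unresolved and constant hazards. The excess is then 2.9 to 4.6 points at 5% dead, 5.5 to 9.0 at 10% and 10.1 to 17.6 at 20%.

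**4. Two groups.** Assume r = 0.08 per day in both, with death shares of 5% and 20%.

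- Group 1: d = 0.08 × 0.05/0.95 = 0.0042, F = 82.9%, true recovery 0.95 × 82.9% = 78.8%.
- Group 2: d = 0.08 × 0.20/0.80 = 0.0200, F = 87.8%, true recovery 0.80 × 87.8% = 70.2%.
- One minus Kaplan-Meier in both: 1 − exp(−0.08 × 21) = 81.4%.

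A true gap of 8.6 points vanishes from the curves. The ordering by deaths needs similar resolution rates. In the table, s = 10% with F = 90% means 9% dead and an excess of 6.4, while s = 20% with F = 60% means 12% dead and an excess of only 4.0.

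**5. Tests.** In 5,000 simulated trials of the two-group case (two-sided 5%), a Gray-type test rejected in 6.4%, 8.7% and 12.5% at 12, 25 and 50 per group. Log-rank rejected in 5.4%, 6.0% and 5.5%. The gain is in the curve, not in the test.

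**The case against.** The strongest reply is that the plan announces neither a proportion recovered nor a rule that deaths are censored. Both are inferences from how these methods are normally used. That is right, and the point is conditional for that reason. A reader might infer that the plan does censor deaths; the text is silent, and that reading is not supported. It remains true that a curve of time to resolution, offered as information on recovery, will be read as a proportion recovered.

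A reader might also infer that deaths will be mistaken for dropout, because reporting in hospital is optional and Aim 1a expects only more than half of prompts to be completed. The documents do not support this as stated:

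- The Aim 1a figure is an average over all prompts in 24 weeks, and Section D reports 82% to 87% completion under similar protocols.
- Staff follow completion remotely and contact participants who do not respond (Sections D and J), and the app supports check-ins with staff after diagnosis.
- The health record is to be used to resolve gaps in specified outcomes.

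What stands is narrower: the date of death must actually be extracted, and the items shown in Section E do not include it.

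Three further replies have weight. Mortality is reported separately, so deaths are not concealed, although a separate percentage does not correct the curve. The size is almost wholly assumed, and mortality may be well below 20% because monitoring starts in non-emergent patients. The two-group example is built to show the mechanism, and no section suggests such a gap in mortality between demographic groups.

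Finally, any resolution curve needs a defined end of follow-up, and Section D describes that end in two ways. This stands and belongs in the fix.

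**Conclusion.** The omission is real, and under ordinary use of the named method the direction of the bias is known: recovery is overstated. Across the constant-hazard and late-death scenarios, the excess at day 21 is about 0.5 to 3 points at 5% mortality, 1 to 6 at 10% and 1.5 to 12 at the cited upper 20%. It is larger if deaths are early and nearly everyone has resolved or died by then. These figures rest on assumed timing, resolution rates and 25 to 50 positives. At 5% to 10% mortality the excess is usually below one standard error.

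A reader might conclude that the planned group comparison is invalid. It is not: log-rank with deaths censored is a valid test of the cause-specific resolution hazard, though not of the proportion recovered. Nor does the point reach the Aim 1 feasibility results or any decision rule. It is a modest improvement to one secondary Aim 2 description, worth making because it costs little.

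**What to change.** In Section M, show the cumulative incidence of symptom resolution by the Aalen-Johansen estimator, with death before resolution as a competing event, up to a stated analysis horizon. To define that horizon, reconcile the two accounts in Section D: 21 days, or until the participant is no longer symptomatic and/or is released from self-quarantine.

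Where every patient can be followed to the horizon, keeping those who die in the risk set as never resolved until then gives the same curve with the software already planned. The two may differ if some patients, for example those infected near week 24, have shorter follow-up.

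Keep log-rank, labelled as a comparison of cause-specific resolution hazards. Gray's test is optional and has little power at the likely group sizes. With equal death hazards, resolution at 0.08 vs 0.12 per day and 25 per group, the simulation gave 23.5% against 27.0% for log-rank at a 10% death share in the slower-resolving group, and 20.4% against 25.4% at 20%.

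Take vital status and date of death from the health-record extraction already planned, and add date of death to the chart items if the Appendix list lacks it.

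The cost is a few sentences, possibly one chart item, and a slightly lower reported recovery proportion.
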